10.1.12	Conflict of Interest Policy.....	55
10.2	Additional Considerations	56
10.3	Abbreviations	56
10.4	Protocol Amendment History	58
11	REFERENCES.....	59

STATEMENT OF COMPLIANCE

The trial will be carried out in accordance with International Conference on Harmonisation Good Clinical Practice (ICH GCP) and the following:

- United States (US) Code of Federal Regulations (CFR) applicable to clinical studies (45 CFR Part 46, 21 CFR Part 50, 21 CFR Part 56, 21 CFR Part 312, and/or 21 CFR Part 812)

National Institutes of Health (NIH)-funded investigators and clinical trial site staff who are responsible for the conduct, management, or oversight of NIH-funded clinical trials have completed Human Subjects Protection and ICH GCP Training.

The protocol, informed consent form(s), recruitment materials, and all participant materials will be submitted to the Institutional Review Board (IRB) for review and approval. Approval of both the protocol and the consent form must be obtained before any participant is enrolled. Any amendment to the protocol will require review and approval by the IRB before the changes are implemented to the study. In addition, all changes to the consent form will be IRB-approved; a determination will be made regarding whether a new consent needs to be obtained from participants who provided consent, using a previously approved consent form.

1 PROTOCOL SUMMARY

1.1 SYNOPSIS

Title: Adding Trauma-focused Psychotherapy to Ketamine Treatment for Chronic PTSD: A Pilot Study

Study Description: Current treatments for posttraumatic stress disorder (PTSD) do not work for a significant proportion of individuals with PTSD, or work only partially, leaving persistent and disabling residual symptoms. Our research team has led the development of ketamine for the treatment of chronic PTSD. After our initial, proof-of-concept randomized controlled trial (RCT) of a single ketamine infusion in individuals with chronic PTSD showed promising results, we completed the first RCT of repeated intravenous ketamine infusions where individuals with chronic PTSD received a course of six ketamine infusions (vs. active placebo midazolam infusions) and demonstrated a rapid and robust improvement in PTSD symptoms. The median time to loss of response, however, was 27.5 days following the course of infusions, making it imperative to investigate novel approaches aimed at preventing symptom relapse following ketamine treatment. We thus propose a proof-of-concept, open-label pilot study to evaluate the efficacy of adding an evidence-based, brief and scalable trauma-focused psychotherapy, Written Exposure Therapy (WET), to a course of ketamine infusions in maintaining PTSD symptom improvement over time, in

participants with chronic PTSD.. To accomplish this aim, we will enroll individuals who meet DSM-5 criteria for chronic PTSD.

Eligible patients will receive a total of 6 ketamine infusions and 5 WET sessions. The primary outcome will be change in PTSD symptom severity assessed by the Clinician-Administered PTSD Scale for DSM-5 (CAPS-5) from baseline (before the first infusion) to 12 weeks from the start of WET. All participants will be assessed until week 12 following the start of WET. They will complete weekly assessments from baseline until 6 weeks from the start of WET, as well as assessments at 12 weeks from the start of WET. At other time points between 6 and 12 weeks, participants will be assessed weekly, or less frequently as tolerated. Although initial response to ketamine (PTSD and co-morbid depressive symptom improvement) will be assessed after the first four infusions (prior to starting WET), all participants will receive 6 infusions and 5 WET sessions regardless of their initial response to ketamine. Participants will be asked not to make any changes to any concomitant treatment (i.e., medication dosages, psychotherapy) during this period.

Thereafter, participants who remain improved at the 12-week time point (compared to baseline) will then receive additional monthly assessments up to 24 weeks or until loss of this improvement.

We will also evaluate whether extinction learning ability –assessed with a computerized extinction learning task– is associated with PTSD symptom improvement from baseline to 12 weeks from the start of WET. If demonstrated to result in significant and maintained PTSD symptom improvement, this novel combined treatment may represent a promising intervention for individuals with chronic PTSD, deserving further study.

Objectives:

Primary Objective: To evaluate the efficacy of adding WET to ketamine therapy in improving PTSD symptoms from baseline to 12 weeks from the start of WET, in individuals with chronic PTSD .

Secondary Objectives (exploratory): (1) To evaluate improvement in PTSD symptoms from baseline to 6 weeks, and on other measures from baseline to 6 weeks, and from baseline to 12 weeks; (2) To evaluate durability of PTSD symptom improvement beyond 12 weeks in patients who remain improved, up to 24 weeks; (3) To evaluate whether ketamine-induced change in extinction learning is associated with improvement in PTSD symptoms from baseline to 12 weeks from the start of WET.

Endpoints:

Primary Endpoint: Change in PTSD symptom severity assessed by the Clinician-Administered PTSD Scale for DSM-5 (CAPS-5) from baseline to 12 weeks from the start of WET.

Secondary (Exploratory) Endpoints:

- Change in PTSD symptom severity from baseline to 6 weeks from the start of WET, assessed by the CAPS-5.
- Change on other measures, including the Montgomery-Asberg Depression Rating Scale (MADRS), Sheehan Disability Scale (SDS), and Clinical Global Impression severity and improvement (CGI-S and CGI-I), from baseline to 6 weeks, and from baseline to 12 weeks.
- In participants with maintained PTSD symptom improvement after 12 weeks, change on the CAPS-5 and other measures, from baseline to 16, 20, and 24 weeks.
- Additionally, change from baseline to 24 hours after the first ketamine infusion, at each ketamine infusion day, and 24 hours after the 4th infusion, on the Impact of Events Scale (IES-R) and Quick Inventory of Depressive Symptomatology – Self-Report (QIDS-SR), both with past-24-hour recall.

Study Population:	Up to N=15 participants with chronic PTSD will be enrolled in the study. Participants will be aged 18-70 years, male or female, with a current primary diagnosis of chronic PTSD according to DSM-5 and at least moderate current illness severity, as determined by a score of 30 or greater on the CAPS-5. Participants will be recruited from the greater New York City area.
Phase:	2
Description of Sites/Facilities Enrolling Participants:	This will be a single-site study, carried out at the Icahn School of Medicine at Mount Sinai (ISMMS) in New York City, United States.
Description of Study Intervention:	
Ketamine: Participants will receive six (6) intravenous ketamine infusions. All ketamine infusions will be administered by a study physician credentialed for ketamine administration at Mount Sinai, at subanesthetic doses of 0.5 mg/kg over 40 minutes at each administration, and a frequency of three times per week over two consecutive weeks. Participants will also receive 5 WET sessions (the first 2 WET sessions will be interleaved with the last 2 infusions, each on a different day).
 
After four (4) ketamine infusions, participants will begin WET sessions. All participants will receive two additional ketamine infusions, interleaved with 5 WET sessions.
 
Written Exposure Therapy (WET): WET consists of 5 sessions, with the first session lasting 1 hour and each subsequent session lasting approximately 40 minutes. The first session includes psychoeducation about common trauma reactions and the treatment rationale, presented

[figure not shown]
by the therapist. The participant is then given general instructions for completing the trauma narratives and specific instructions for completing the first 30-minute narrative during that first session. All WET sessions begin with the therapist reading the specific writing instructions, clarifying any questions the participant might have, and leaving the instructions with the participant for the 30-minute writing session. Writing instructions begin with a focus on the details of the trauma and then shift to the meaning of the trauma event. After 30 minutes of writing, the therapist stops the writing and conducts a 5-10 minute check-in regarding how the writing session went for the participant.

Study Duration: The study is anticipated to take place over 48 months.

Participant Duration: Participants will be in the study for up to 27 weeks. See schema in section 1.2 below for a summary.

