1.3 SCHEDULE OF ACTIVITIES (SOA)

Procedures	Screening	Baseline	Ketamine Infusions	24 hour Follow-Up Visit	Assessment of Response to Ketamine	WET Sessions	Weekly Assessment Until 12 weeks	Monthly Assessment Until Loss-of-Response
	Day - 28 to 0	Visit 1a, Day 1	Visit 1a-9; Days 1, 3, 5, 8, 11, 12	Visit 1b, Day 2	Visit 5, Day 9	Visit 6-12, Days 10, 12, 16, 18, 22	Visits 10, 13-23, Days 12, 19, 26...	Visits 23-26, Days 33...
Informed consent	x							
Demographics	x							
Medical history	x							
SCID-5	x							
CAPS-5	x	x			x		x	x
MADRS	x	x			x		x	x
WTAR	x							
MoCA	x							
IES-R		x	x	x	x			
QIDS-SR		x	x	x	x			
PCL-5	x	x			x		x	x
MOS-5		x					x ¹	
CES		x					x ¹	
PACT		x					x ¹	
CTQ	x							
TLEQ	x							
SDS	x	x		x	x		x	x
HMS			x ²					
PIQ			x ²					
C-SSRS	x	x			x		x	x
CADSS		x	x					
BPRS		x	x					
YMRS		x	x					
Extinction Learning Task	x				x			
CGI	x	x	x	x	x		x	x
Concomitant medication review	x	x	x	x	x		x	x
PRISE	x	x	x	x	x		x	x

Adverse event review and evaluation	x	x	x	x	x	x	x	x
Physical exam (including height and weight)	x							
Vital signs	x		x					
Weight	x		x					
EKG	x							
Routine labs	x							
Plasma ketamine and norketamine levels			x ³					
Urine pregnancy test	x		x					
Urine drug screen (UTOX)	x		x					
Ketamine infusion (0.5 mg/kg)			x					
Written Exposure Therapy (WET)						x		
Complete Case Report Forms (CRFs)	x	x	x	x	x	x	x	x

¹Visit 14 and 23 only

²only at Infusions 1 and 2

³only at Infusion 1

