4.4 END OF STUDY DEFINITION

A participant is considered to have completed the study if he or she has completed all phases of the study shown in the Schedule of Activities (SoA), Section 1.3. For all participants, the earliest end of study will be the 12-week follow-up assessment. For participants who remain improved at this 12-week assessment, the end of study will be their final follow-up visit (depending on time to loss of this improvement).

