The **Columbia Suicide Severity Rating Scale (C-SSRS)** is a comprehensive, semi-structured interview measure commonly employed in clinical trials. The C-SSRS measures the full spectrum of suicidality, including passive and active suicidal ideation, suicidal intent, and suicidal behaviors.⁶⁰ All study subjects will be assessed for suicidal ideation and behavior by the study PI or other trained member of the study team. Both past-month and lifetime versions of the C-SSRS will be administered at study screening. Individuals who score a 4 or greater on the past-month suicidal section, or who have engaged in any suicidal behavior in the past month, will be excluded and referred promptly for clinical care. Our clinicians and staff at the Depress Anxiety Center all undergo formal web-based training on administering the C-SSRS, and have extensive experience in its utilization. The Center has established SOPs for handling suicidality. For patients who do not show suicidality at the described threshold and proceed to participate in this study, the C-SSRS will be administered at each assessment time point (until 12 weeks, and then monthly up to 24 weeks or until loss of response), to assess for suicidal ideation and participant safety throughout the study. Participants with scores of 4 or greater at any point during the study will be exited from the study and promptly referred for clinical care.

The **Sheehan Disability Scale (SDS)** is a brief, 5-item self-report scale that assesses functional impairment in domains of work or school, social life, and family life.⁵⁹ Higher scores on this scale represent higher functional impairment. This scale will be administered at screening, and then at each assessment time point (weekly until 12 weeks, and then monthly up to 24 weeks or until loss of response).

The **Clinical Global Impression –Severity and –Improvement scales (CGI-S and CGI-I)** are among the most widely used brief assessment tools in psychiatry and clinical trials.⁸² The CGI-S will be administered

at screening and baseline prior to any infusions, and both the CGI-S and the CGI-I will be administered at each assessment time point (weekly until 12 weeks, and then monthly up to 24 weeks or until loss of response) by the PI or another study clinician, to determine global severity of psychiatric illness.

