8.3.4 TIME PERIOD AND FREQUENCY FOR EVENT ASSESSMENT AND FOLLOW-UP

The occurrence of an adverse event (AE) or serious adverse event (SAE) may come to the attention of study personnel during study visits and interviews of a study participant presenting for medical care, or upon review by a study monitor.

All AEs including local and systemic reactions not meeting the criteria for SAEs will be captured on the appropriate case report form (CRF). Information to be collected includes event description, time of onset, clinician's assessment of severity, relationship to study product (assessed only by those with the training and authority to make a diagnosis), and time of resolution/stabilization of the event. All AEs occurring while on study must be documented appropriately regardless of relationship. All AEs will be followed to adequate resolution.

Any medical condition that is present at the time that the participant is screened will be considered as baseline and not reported as an AE. However, if the study participant's condition deteriorates at any time during the study, it will be recorded as an AE.

Changes in the severity of an AE will be documented to allow an assessment of the duration of the event at each level of severity to be performed. AEs characterized as intermittent require documentation of onset and duration of each episode.

Drs. [name], [name], [name], or [name] will record all reportable events with start dates occurring any time after informed consent is obtained until 7 (for non-serious AEs) or 30 days (for SAEs) after the last day of study participation. At each study visit, the investigator will inquire about the occurrence of AE/SAEs since the last visit. Events will be followed for outcome information until resolution or stabilization.

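### Section 8.3.4 records AEs for 7 days and SAEs for 30 days after the last study day, but no contact is scheduled in that window, so new events, chiefly in early exits, are found only passively

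*Combined protocol and SAP*

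**What the plan says.** **The window.** Section 8.3.4 has the study physicians record events from consent "until 7 (for non-serious AEs) or 30 days (for SAEs) after the last day of study participation".

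**How events are sought.** The same section gives one active method: "At each study visit, the investigator will inquire about the occurrence of AE/SAEs since the last visit". It also notes that events may surface when a participant seeks medical care or when a monitor reviews records.

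**The last contact.** For everyone, the synopsis states: "All participants will be assessed until week 12 following the start of WET". Participants still improved at that point have "additional monthly assessments up to 24 weeks or until loss of this improvement". Section 4.4 ties the end of study to these visits: "For all participants, the earliest end of study will be the 12-week follow-up assessment", and for those still improved it is their last follow-up visit. The final column of the Schedule of Activities is "Monthly Assessment Until Loss-of-Response"; nothing comes after it.

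**Early exits.** Under the C-SSRS entry in section 8.1, a participant scoring 4 or more during the study "will be exited from the study and promptly referred for clinical care". Section 7.2 lists other grounds on which an investigator may withdraw a participant. Neither section describes a study contact after exit.

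**The concern.** The protocol undertakes to record events in a period when, by its own schedule, nobody asks about them. Inquiry at a visit looks back to the previous visit. The last visit therefore covers the time up to the last study day, and no later visit looks back over the following 7 or 30 days.

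At stake is whether SAE ascertainment is complete in a pilot of up to 15 participants. If no event is recorded after exit, a reader cannot tell whether none occurred or nobody asked. Expedited DSMB review (10.1.6) and the sponsor's FDA notification (8.3.6) both depend on the team learning of the event. The people for whom this counts most are those who leave the study close to treatment, since the 30 days then lie near exposure and the reason for leaving may itself concern safety.

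**Working it through.** The plan gives no figure to reproduce. The check is calendar arithmetic followed by a comparison of sections.

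**Inputs, as printed in the Schedule of Activities (1.3):** WET starts on Day 10; the last WET session is on Day 22; the last infusion is on Day 12; the response assessment is on Day 9, one day after the Day 8 infusion. **From 8.3.4:** 7 days for AEs, 30 days for SAEs.

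**Formulas.** Last visit day = 10 + 7 × weeks. Window end = last study day + 7 (AE) or + 30 (SAE).

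- *Last visit at week 12:* 10 + 84 = Day 94. AE window to Day 101, SAE window to Day 124. Distance from the last infusion: 94 − 12 = 82 days; from the last WET session: 94 − 22 = 72 days.
- *Last visit at week 24:* 10 + 168 = Day 178. AE window to Day 185, SAE window to Day 208. Distance from the last infusion: 178 − 12 = 166 days.
- *Exit on Day 9:* SAE window to Day 39.
- *Exit on Day 22:* SAE window to Day 52.

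Scheduled contacts inside any of these windows: none.

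**Sensitivity to the printed days.** The weekly column starts at Day 12 and covers twelve visits (10 and 13 to 23). Run on without a break, its twelfth visit falls on 12 + 7 × 11 = Day 89, which is 77 rather than 82 days after the last infusion. The conclusion is the same.

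**Does another section close the gap?**

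- *8.3.4 and 8.2* require known events to be followed until resolved or stable, and longer-lasting side effects to be assessed weekly until they resolve. Both concern events already identified.
- *6.1.2* describes an exit visit for completers. It deals with transition of care and is the end of participation, not a contact after it.
- *7.3* sets out telephone attempts, but these are triggered by missed visits, not by exit.
- *2.3.3* offers more contact or more frequent visits to people at suicide risk. These are care options, not a scheduled safety contact.
- *5.1 and 2.3.3* provide a Treatment Contract person and an emergency contact. They may call the team or be called in an emergency; no routine inquiry is planned.

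None of these actively looks for a new event after the last study day.

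**The case against.** The case against giving this much weight has five parts.

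**Exits for suicidality.** A reader might infer that someone exited on Day 9 is wholly unobserved until Day 39. The documents do not support that. Entry requires a past-month C-SSRS ideation score below 4, so a later score of 4 or more is normally an increase, and 8.3.5 counts ideation that has grown in frequency or severity since baseline as an AE. Section 8.3.4 then requires follow-up until that event resolves. This stands. What is left is new events unrelated to the one being followed.

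**Stopping treatment.** Section 7.1 keeps participants who stop ketamine or WET in the study with their remaining procedures. This also stands: the gap concerns exit from the study, not from treatment.

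**Other routes.** Presentation for care, monitor review, nominated contacts and permission to approach providers (6.1.2, 10.1.1.2) mean participants are not simply lost from view. That is true, but every one of these is passive or discretionary.

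**Bias in results.** A reader might infer that a reported SAE count will be too low. Section 9.4.4 plans no SAE-count analysis, and the event rates in 9.4.1 count patient-time to study exit or to the end of the period of interest. With one arm, no comparison is distorted. The issue is incomplete ascertainment, not a biased estimate.

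**Participant duration.** A reader might also take "Participants will be in the study for up to 27 weeks" to be wrong. The starting point of that count is not given, and the flow diagram it refers to is not reproduced. From Day 1, 27 weeks runs to 1 + 189 = Day 190, which contains the week-24 visit on Day 178. No error is established, and the 30-day window lies by definition after participation ends.

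**Conclusion.** The point holds in a limited form. Section 8.3.4 defines a post-study window that the Schedule of Activities and section 4.4 give no means of observing actively. Formally this affects every treated participant. In practice the consequence is small for completers, whose window opens 82 days or more after the last infusion with WET starting on Day 10. It is larger for those exited or withdrawn during or soon after the infusions. For them, known AEs are followed but new SAEs are not sought.

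The number of early exits is not known in advance, and the documents give no post-exit event rate, so the number of SAEs that might be missed cannot be estimated. The conclusion assumes that the manual of procedures, which is not among the documents, adds no such contact. If it does, the Schedule of Activities should still show it.

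**What to change.** Add one entry to the Schedule of Activities: a telephone AE/SAE review 30 days after the last study day for every treated participant, including those exited or withdrawn early unless they refuse contact. Cross-reference it in 8.3.4. State there that the call does not itself count as the last study day, so that the window is not extended by the contact that closes it. A call at 30 days also covers the 7-day AE window, since it can ask for onset dates.

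The cost is at most 15 calls by existing staff on the enrolment ceiling in 9.2 (16 on the figure in 5.5), plus protocol and consent wording. It needs no clinic visit or new instrument, and changes no exit criterion or treatment rule. If the sponsor prefers not to add the call, 8.3.4 should at least say that capture after the last study day is passive.

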1.2 SCHEMA

Figure 1. *Flow diagram*

1.3 SCHEDULE OF ACTIVITIES (SOA)

Procedures	Screening	Baseline	Ketamine Infusions	24 hour Follow-Up Visit	Assessment of Response to Ketamine	WET Sessions	Weekly Assessment Until 12 weeks	Monthly Assessment Until Loss-of-Response
	Day - 28 to 0	Visit 1a, Day 1	Visit 1a-9; Days 1, 3, 5, 8, 11, 12	Visit 1b, Day 2	Visit 5, Day 9	Visit 6-12, Days 10, 12, 16, 18, 22	Visits 10, 13-23, Days 12, 19, 26...	Visits 23-26, Days 33...
Informed consent	x							
Demographics	x							
Medical history	x							
SCID-5	x							
CAPS-5	x	x			x		x	x
MADRS	x	x			x		x	x
WTAR	x							
MoCA	x							
IES-R		x	x	x	x			
QIDS-SR		x	x	x	x			
PCL-5	x	x			x		x	x
MOS-5		x					x ¹	
CES		x					x ¹	
PACT		x					x ¹	
CTQ	x							
TLEQ	x							
SDS	x	x		x	x		x	x
HMS			x ²					
PIQ			x ²					
C-SSRS	x	x			x		x	x
CADSS		x	x					
BPRS		x	x					
YMRS		x	x					
Extinction Learning Task	x				x			
CGI	x	x	x	x	x		x	x
Concomitant medication review	x	x	x	x	x		x	x
PRISE	x	x	x	x	x		x	x

Adverse event review and evaluation	x	x	x	x	x	x	x	x
Physical exam (including height and weight)	x							
Vital signs	x		x					
Weight	x		x					
EKG	x							
Routine labs	x							
Plasma ketamine and norketamine levels			x ³					
Urine pregnancy test	x		x					
Urine drug screen (UTOX)	x		x					
Ketamine infusion (0.5 mg/kg)			x					
Written Exposure Therapy (WET)						x		
Complete Case Report Forms (CRFs)	x	x	x	x	x	x	x	x

¹Visit 14 and 23 only

²only at Infusions 1 and 2

³only at Infusion 1

